2.3 Study Design	
TYPE OF STUDY: Multi-center: "Infanta Leonor" Teaching Hospital (HUIL), National Microbiology Center–Carlos III Health Institute (CNM-ISCIII), and the Harm Reduction Unit (HRU) (Madrid Positivo and the Anti-Drug Agency).
 
DURATION OF THE STUDY: 24 months.
 
DESIGN OF THE STUDY: Cross-sectional.
 
SCOPE OF THE STUDY: The study population comprises persons who visit the Cañada Real Galiana shantytown on the outskirts of Madrid, where 90% of illegal drugs in the region are sold and consumed. It is estimated that between 4000 and 6000 people per day visit the shantytown for their dose. The regional government's Anti-Drug Agency has a mobile HRU operating daily in the area. The unit provides screening tests to anyone who is willing to take them, regardless of whether they are already aware of their serological status or not. Screening includes education on prevention of HCV infection and other transmissible diseases.
 
PHASES OF THE STUDY
 
1) PHASE I: Setting and calibration of the laboratory techniques needed to carry out the study. The screening method will be validated with dried blood spots from Whatman 903™ cards taken from volunteer patients at HUIL. The results will be compared with the results of a venous blood sample taken from the same individual at HUIL. The sensitivity (Se), specificity (Sp), positive predictive value (PPV), and negative predictive value (NPV) of the diagnostic tests will be determined.
 
2) PHASE II: Screening for HCV and other viruses (HIV, HBV, HDV) using dried blood samples on Whatman™ cards in subjects from Cañada Real based on the results of the laboratory tests performed in phase I. The data and samples will be collected by the HRU. All the samples collected will be sent by courier to the CNM-ISCIII for processing and analysis.
 
3) PHASE III: Evaluation of the effectiveness of the intervention. Subjects who had a positive result in the screening performed in Cañada Real Galiana will be contacted and offered the possibility of referral to HUIL, where they will have access to standard confirmation tests. Here, test accuracy will be evaluated at population level. Patients will have access to HCV treatment and will be followed for assessment of the impact of the program on patients' health (referrals to health centers, percentage of treated patients, and the percentage of virological response). As part of the harm reduction program patients will be screened periodically after therapy to detect HCV reinfection.
 
COLLECTION AND PROCESSING OF SAMPLES
 
Biological samples will be collected according to the study protocol as dried blood spots on Whatman 903 cards (50-75 µl of blood). The blood samples obtained will be processed according to the protocol for handling samples set out in Annex 1 of the

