Participants will be given an information leaflet and a specific informed consent form. Samples will be processed according to the study protocol (Annex 1). Clinical and epidemiological data will be recorded in a database that can be accessed by researchers from the HUIL and the CNM-ISCIH. The variables shown in section 2.4 will be recorded. This file has been included in the Register of Data Files of the ISCIH.

ELISA: A disc with a sample of dried blood will be placed in a microtube containing 300 μl of 0.5% buffer solution (PBS/BSA) and processed at $4-8^{\circ}\text{C}$ for 18-24 hours. After incubation, elutes from the dried blood samples will be tested for the presence of antibodies against HCV, HIV, and HDV, as well as for HBV surface antigen (HBsAg). Negative samples will not undergo further testing and will be considered non-infected. Positive samples will be tested using real-time PCR to confirm the positive results.

Real-time PCR: Nucleic acids will be extracted using the DSP virus pathogen kit (QIAGEN, Hilden, Germany). The samples will be stored at -80°C until use. A specific HCV test will be performed to confirm active HCV infection (HCV-RNA positive) on a Rotor Gene Q unit (QIAGEN).

PHASE II: SCREENING AT CAÑADA REAL GALIANA

Screening for HCV and the other viruses (HIV, HBV, and HDV) covered by this project will take place at Cañada Real Galiana. Screening will be conducted by nursing personnel hired specifically for that purpose. An active search will be made for

individuals who come into the shantytown from outside, and the detection test will be offered to everyone regardless of whether or not their serological condition is already known. Selection of individuals for screening will be random and consecutive.

Nursing personnel will generally be accompanied by an educator from the HRU. PWID will be offered information on prevention and the importance of early diagnosis and referral to health centers.

Information will then be provided on the goals of the study, and persons who agree to take part will be required to sign an informed consent form, provide contact data for subsequent location, and provide basic social and demographic data and information on their consumption habits. Regardless of whether or not individuals agree to take part in the study, they will all be given a card containing basic information on prevention and contact data for the internal medicine department of HUIL and the HRU.

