Data will be recorded on social and demographic details, the consumption habits of each PWID, and the acceptability of the screening test. All data will be recoded in the database by the nurse or the educator using a mobile device with Internet capability and REDCap software. Informed consent forms will be kept in the files of the researcher at the HRU office.

The Whatman™ cards will be stored in a portable refrigerator after processing (see below) and shipped via courier to the National Microbiology Center (CNM) for analysis.

If a test result is positive, the patient will be contacted and offered referral to a specialist health care center in accordance with the study algorithm to confirm the result and assess whether monitoring should begin. All subjects included in the study may contact the medical department or the Harm Reduction Unit directly to make an appointment and collect the results of their tests.

PHASE III: EFFECTIVENESS OF THE INTERVENTION

Evaluation of the effectiveness of the intervention. Drug users who test positive will be contacted and offered the possibility of referral to a specialist health care center, where access to standard confirmation tests used in hospital and access to treatment will be offered. As specified in the consent form, if a patient with a positive result cannot be contacted, regional registries and hospital patient data will be used to find the patient.

Once the patient has been found or contacted, referral to HUIL will be offered to him. The harm reduction team accompanies the drug user to hospital to be evaluated by a practitioner with expertise in assessment of liver disease severity and HCV treatment. In the first visit to the hospital, a part from the medical history and physical examination, a blood test and a Fibroscan® will be performed. These blood tests will confirm the results from the screening for HCV in Cañada Real.

At this point, all PWID will be offered substitution therapy with methadone and referral to a detoxification center. If the patient accepts, he will then be taken to a detox center to start HCV therapy and where he will stay for an average of six months. If the patient does not accept referral to a detox center, the mobile harm reduction unit will administer therapy (directly observed therapy) to him and will be in charge off his follow up in the shantytown.

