In contrast with the rapid tests, sample processing is centralized, so results are not available immediately. Given that screening is performed in an unfavorable setting and on an outpatient basis, a series of problems could arise, as follows: (1) errors in the processing of samples (eg, insufficient sample volume contamination, loss); (2) difficulties in contacting participants once the results are available; and (3) the assumption that although a significant percentage of consumers will consent to screening, many will refuse referral to a health center for confirmation of diagnosis and treatment.

GENERAL TASKS

1. Administrative tasks: Classification by the Spanish Agency for Medicines and Medical Devices (AEMPS) and presentation to the Clinical Research Ethics Committee (CEIC).
2. Contracting of IT services. Design of online data collection forms.
3. Final design of protocol and informed consent forms.
4. Design of database and adaptation of online data collection forms.
5. Initial meeting of researchers.
6. Six-monthly teleconferences for researchers.
7. Phase 1: Recruitment, collection of informed consent forms, collection of

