2.6 Study Duration

2.7 Statistical Analysis and Sample Size Justification

PHASE I

Once all subjects have been included, the results from the Whatman 903 cards will be compared with those obtained by venipuncture at HUIL. Diagnostic performance will be assessed by calculating the area under the ROC curve (AUROC) for each virus. The Se, Sp, PPV, and NPV for each virus will also be calculated.

PHASE II

Sample size: Assuming that around 10,000 people visit Cañada Real Galiana on different days, a sample size of 930 randomly selected subjects will suffice to estimate, with a 95% confidence interval and a precision of ± 3 percentage points, a

population percentage considered to be around 60%. A replacement rate of 0% has been anticipated.

PHASE III

In order to evaluate the effectiveness of the intervention, the accuracy of HCV tests will be calculated at the population level (AUROC, Se, Sp, PPV, and NPV), as will the percentage of patients arriving at the clinic, the percentage of patients treated, and the percentage of patients cured of hepatitis C. The incidence of HCV reinfection will be assessed using a Kaplan-Meier survival method. In addition, the effectiveness of the intervention for HIV, HBV, and HDV infection will be evaluated.

Statistical Methods

The statistical analysis will be performed using IBM SPSS Statistics for Windows, Version 22.0 (IBM Corp, Armonk, New York, USA) and the R statistical package, version 3.2.2 (GNU General Public License). All tests will be two-tailed, with p-values of <0.05 considered statistically significant.

An assessment will be performed to determine the percentage of patients who are positive at screening, are referred to a health center, have their diagnoses confirmed, and are treated at the end of the study. Factors associated with virus transmission, lack of referral to a health center, and HCV treatment will also be analyzed.

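### Phase III promises population-level Se, Sp, NPV and AUROC for the HCV card test but plans reference testing only for screen-positives, so without further assumptions only PPV among attendees is estimable

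*Combined protocol and SAP*

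**What the plan says.** For Phase III, section 2.7 states that "the accuracy of HCV tests will be calculated at the population level (AUROC, Se, Sp, PPV, and NPV"). Section 2.3 (Phases of the study, Phase III) places this at the hospital confirmation step: "Here, test accuracy will be evaluated at population level".

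The route to that step starts from a positive card:

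- Section 2.3, outline of Phase III: "Subjects who had a positive result in the screening performed in Cañada Real Galiana will be contacted and offered the possibility of referral".
- Section 2.3, detailed Phase III text: "Drug users who test positive will be contacted and offered the possibility of referral to a specialist health care center".
- The general task list (item 19) plans contact with those who tested positive.
- Registries and hospital records are a tracing tool for the same group: "if a patient with a positive result cannot be contacted, regional registries and hospital patient data will be used to find the patient".

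Participants in general have one other route: "All subjects included in the study may contact the medical department or the Harm Reduction Unit directly to make an appointment". Its stated purpose is to collect results; no reference test is mentioned.

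The limitations paragraph expects incomplete verification even among positives: "many will refuse referral to a health center for confirmation of diagnosis and treatment". Section 2.7 describes no verified sample of negatives and no correction for partial verification.

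**The concern.** Sensitivity and NPV need a count of infected people whose card was negative. Specificity and NPV need a count of uninfected people whose card was negative. AUROC needs both. All of these come from reference results in card-negative people, and the readable text provides no representative set of them. This is verification bias.

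The error runs in a flattering direction for the figure that matters most in screening. Sensitivity computed from people who mostly entered because they were positive will be near 100%, however many infections the card misses. The protocol itself names reasons for misses: a PCR detection limit of about 1000 IU/mL, and insufficient or damaged samples in the field. Phase III as described would see few of them.

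**Working it through.** **Inputs.** Section 2.7, Phase II: 930 subjects, a percentage of about 60%, ±3 points, 95% confidence, about 10,000 visitors. Section 2.3, limitations: 94% for both Se and Sp. Neither the 60% nor the 94% is tied to a marker (antibody or RNA). Applying both to the target HCV state is an assumption. So is verification of all positives and no negatives.

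**The plan's own figure.** With finite-population correction, n = N z² p(1−p) / [d²(N−1) + z² p(1−p)]. With N = 10,000, z = 1.96, p = 0.60 and d = 0.03, this is 9,219.5 / (8.999 + 0.922) = 929.3, hence 930. The figure reproduces. It is sized for a prevalence; no sample size or precision is given for Phase III accuracy.

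**Step 1: the full expected table.**

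- TP = 930 × 0.60 × 0.94 = 524.5
- FN = 930 × 0.60 × 0.06 = 33.5
- FP = 930 × 0.40 × 0.06 = 22.3
- TN = 930 × 0.40 × 0.94 = 349.7

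That is 546.8 card-positive and 383.2 card-negative people. PPV = 524.5/546.8 = 95.9%. NPV = 349.7/383.2 = 91.3%. AUROC at a single cut-off = (Se + Sp)/2 = 0.94.

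**Step 2: only positives verified.** Se = 524.5/(524.5 + 0) = 100%. Sp = 0/(0 + 22.3) = 0%. NPV = 0/0. AUROC = (1 + 0)/2 = 0.50. If a random fraction of positives attends, TP and FP shrink by the same factor: these four results do not change, and PPV stays 95.9% in expectation.

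**Step 3: would a poor card show up?** Take a true Se of 60% (a hypothetical value). Missed infections rise from 33.5 to 930 × 0.60 × 0.40 = 223.2. Computed Se is still 100%. PPV = 0.36/(0.36 + 0.024) = 93.8%, a fall of about 2 points.

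**Step 4: what the same data are compatible with.** Hold TP = 524.5, FP = 22.3 and 383.2 negatives, and let f be the unknown infected share of the negatives. Then Se = 524.5/(524.5 + 383.2f), Sp = 383.2(1−f)/[383.2(1−f) + 22.3], and NPV = 1−f.

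| f (assumed) | Se | Sp | NPV | AUROC |
|---|---|---|---|---|
| 0% | 100% | 94.5% | 100% | 0.97 |
| 10% | 93.2% | 93.9% | 90% | 0.94 |
| 30% | 82.0% | 92.3% | 70% | 0.87 |
| 50% | 73.2% | 89.6% | 50% | 0.81 |

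Nothing in the planned data selects a row. Counting negatives as uninfected by rule selects the first row, with Se and NPV of 100% by construction. Sp moves much less than Se or NPV, but it is not identified either.

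**Step 5: other prevalences.** At an assumed 40% or 80%, PPV is 91.3% or 98.4% and true NPV is 95.9% or 79.7%. The Step 2 results for Se, Sp, NPV and AUROC are the same.

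**The case against.** A reader might infer that no HCV-negative person ever receives a reference test, so that the four measures are beyond reach and Sp would literally be reported as 0%. The documents do not support that.

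- **The card test has two steps, and the meaning of positive is not defined.** Cards are tested for antibody, and positives then go to PCR. The text does not say whether an antibody-positive, RNA-negative card leads to referral. If it does, those people get hospital RNA results (a listed Phase III variable), and an RNA table has a negative row. If 60% is antibody prevalence and 10–40% of those infections have resolved (both assumptions), that is 558 × 0.10 = 56 to 558 × 0.40 = 223 truly RNA-negative people who could be verified. Accuracy of the RNA step among antibody-positives could then be estimated.
- **Positives for HIV, HBV or HDV may also attend** and have HCV tests recorded.
- **The laboratory rule for negatives proves less than it seems.** The sentence "Negative samples will not undergo further testing and will be considered non-infected" stands in the Phase I section and keeps ELISA-negative cards from PCR. Phase I participants have paired venous samples, so it does not show that card-negatives lack a reference test.
- **The flowchart figures are not available here.** A verification step drawn only there cannot be excluded; the text mentions none.
- **The study does examine sensitivity.** Phase I compares cards with venous samples in 150 people. Objective 3 defines effectiveness by referral, treatment and cure, which this point does not touch.

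All of this stands, and it limits the wording. It does not rescue the population-level figures. HCV-negative attendees are a selected group, infections missed at the antibody step stay largely unverified, and Phase I recruited hospital patients and healthy companions, not the screened population.

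**Conclusion.** The point holds in this form: population-level Se, Sp, NPV and AUROC cannot be estimated from the planned Phase III data without further assumptions. PPV among attendees is directly estimable if attendance is unrelated to true status. In the illustration, computed Se is 100% whether the true value is 94% or 60%, while data of the same form are compatible with Se from 100% down to 73% as the infected share of negatives goes from 0% to 50%. The extreme values (Sp 0%, NPV undefined, AUROC 0.50) apply only when no card-negative person is verified. The sizes also rest on reading 60% and 94% as figures for one HCV marker. The direction does not depend on those numbers; it follows from who is offered the reference test. The sample size of 930 is not at fault.

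**What to change.** In section 2.7, Phase III, replace the five listed accuracy measures with: *PPV with exact 95% CI among screen-positives tested at HUIL*. State the marker (antibody or RNA) and which card result counts as positive. Report the number verified out of the number positive, and the days between card and venous sample. The last item needs a date for the hospital sample, which the listed Phase III variables do not include.

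In section 2.3, Phase III, reword the sentence "Here, test accuracy will be evaluated at population level" to match.

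If antibody-positive, RNA-negative people are referred, accuracy of the RNA step may be reported, labelled as conditional on antibody-positive attendees. Any population NPV should be labelled a projection from Phase I Se and Sp at the Phase II prevalence, with a caution about spectrum bias because Phase I used hospital patients and healthy companions.

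The cost is wording and one date field. The downside is that the unsupported population-level figures are no longer reported.

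If the sponsor wants to keep them, the alternative is to reference-test a random sample of card-negatives and weight back (Begg-Greenes). With 100 negatives verified, and assuming 60% prevalence, 94%/94% and half of the positives verified at random, simulated 95% ranges are Se 90.2–97.4%, Sp 90.5–97.2% and NPV 85–96%. At 40% and 80% prevalence the Se ranges are 88.2–98.6% and 91.6–96.3%. This costs added venous sampling in a hard-to-reach group.
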